### **2.3 Monitoring procedures**

No source data verification will be done.

Quality data control of all data captured into the online database will be performed by coherence analysis by Club Hernie authorized representative.

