### **1.1 Primary Objective**

Evaluate the incidence of peri-operative and post-operative complications, with post-operative evaluations occurring, at discharge , 1 week (D1 and D8 follow up), 1 month (D30 follow up), 1 Year and 2 Year follow up after primary and incisional abdominal wall hernia surgeries using Symbotex™ Composite Mesh by open or laparoscopic approach (such as anticipated device related complications such as pain, recurrence, complications related to adhesions, wound complications, other postoperative complications, SAE...).

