One hundred patients will be followed using the online database for registration and patient outcome measurements, including pre-operative, operative, discharge, post-operative course (D1 and D8 follow up), 1 month (D30 follow up), 1 Year and 2 Year follow up. The pain nurses will carry out the pain evaluation on the day of surgery (D0) and on postoperative day 1 (D1) (by phone call in case of day surgery). Pain on day 8 is assessed either during clinical exam or by phone if the patient is already discharged. Patients will be given an appointment for a clinical visit on day 30 (D30 follow up). The post-operative visit at 1 month (D30 follow up) is the standard of care for patient follow up following primary abdominal wall and incisional hernia surgeries.

For long-term follow up, two sets of self-administered QOL questionnaires will be administered by phone call at 1 Year and 2 Year follow-up.

Follow up by phone questionnaires will be performed by a Clinical Research Associate mandated by Club Hernie, independent from the operative surgeons

The Clinical Research Associate will enter into the database answers from the patient-based self-assessment questionnaires.

The answers will be registered without any medical adjustment into the database. The patients who complain of any trouble will be invited to have a clinical visit at the surgeon's office. The correlation between the patient's answer and clinical assessment and physical examination will then be determined.

A patient will be considered lost to follow-up after 5 failed attempts of meticulous postal reminders and phone calls at various times, therefore minimizing the non-response bias.

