### **5.6 1 month (D30) Follow up**

- Pain assessment measured with VAS\* score
- \* Mid pain for VAS score between 0 and 3; Moderate pain for VAS score > 3 and < 6 ; Severe pain for VAS scores > 6.
- Post-operative complications (including SAEs)
- Quality of Life « QoL » Questionnaire (Appendix C)

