### **Statistical Analysis Plan Summary**

The analysis will be performed for primary and secondary endpoints, all data will be analyzed, according to the methods previously described in the general considerations section.

- 1) Descriptive Analysis of patients registration and outcomes measurement
- 2) Baseline and Demographic Data Analysis
- 3) Operative Data Analysis
- 4) Primary endpoints measured within 1month, 1 Year and 2 Year follow-up
  - a. Peri-operative complications
  - b. Post-operative complications such as anticipated device related complications as pain, recurrence, complications related to adhesions, wound complications, other postoperative complications, SAEs...
  - c. All complications
- 5) Secondary endpoints analysis during the whole follow-up
  - a. Surgical technique and mesh fixation
  - b. Operative time descriptive analysis
  - c. Ease of use / mesh manipulability assessment by surgeons
  - d. Length of hospital stay analysis
  - e. Quality of life and patient satisfaction analysis
  - f. Surgeon satisfaction

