**9- Have you had a re-operation on your abdominal wall?**

- No
- Yes (if so please specify)

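### Early complications that are never entered have no reliable check, and the independent 1- and 2-year calls, as written, do not supply one

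*Protocol*

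**What the plan says.** **Endpoint.** Section 1.1 sets out to "Evaluate the incidence of peri-operative and post-operative complications" from surgery to 2 years, and names wound complications and complications related to adhesions among them. Section 6.2 lists peri-operative, post-operative and all complications under "Primary endpoints measured within 1month, 1 Year and 2 Year follow-up".

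**Early recording.** Peri-operative events are collected on the day of surgery (5.2), and post-operative complications at discharge (5.3) and at 1 month (5.6). Sections 2.2 and 7.2 restrict database accounts to surgeon members. Section 2.2 describes the database as a tool with which they follow their own practice and results. Before 1 year, the only named assessor other than the surgeon is the pain nurse, for the pain score on the day of surgery and the day after.

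**Checking.** Section 2.3 says "No source data verification will be done", and then: "Quality data control of all data captured into the online database will be performed by coherence analysis by Club Hernie authorized representative".

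**Late contacts.** The 1- and 2-year phone questionnaires are done by a "Clinical Research Associate mandated by Club Hernie, independent from the operative surgeons", who enters the answers (2.2). The Appendix C form for these calls covers firmness of the abdomen, a new hernia or bulge, current symptoms and their features, re-operation ("Have you had a re-operation on your abdominal wall") and the overall result. Sections 5.7 and 5.8 also list post-operative complications, including SAEs, at these contacts. Their footnotes say that patients who complain are invited to see the surgeon, and that complications and the pain score are then recorded.

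**The concern.** A coherence check compares entries with one another. It can find a discharge date before the surgery date. It has little to work with when a wound infection was treated and simply not entered. With no source verification, completeness then depends on whoever enters the data, apparently a member of the group whose results are being described.

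The protocol does provide an independent contact with every patient who can be reached, but the form used there looks at the present state. A patient whose seroma was drained at week 3, or who was re-admitted at week 6 and recovered, has no question to answer and no current trouble to report. Omissions of this kind push the complication incidence one way, downward, and a larger sample would not remove them. The final report could not say how complete its main result is.

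**Working it through.** **1. The plan's own figure.** Section 6.1 plans on a 5.9% recurrence rate, ±5% precision and a 95% interval:

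n = 1.96² × 0.059 × 0.941 / 0.05² = 85.3, rounded up to 86.

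This agrees with the stated 86. With 15% lost, 100 × 0.85 = 85 patients remain, for a half-width of 5.01 points. The calculation covers sampling error for recurrence only; it makes no allowance for unrecorded events and sets no precision for early complications.

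**2. Which early outcomes have a source besides the surgeon's entry?**

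| Outcome | Other source in the protocol | Compared with the early entry? |
|---|---|---|
| Pain, day of surgery and day after | Pain nurse (2.2, 5.2, 5.4) | Not applicable |
| Symptoms at 1 month | Patient questionnaire, current symptoms only; no independent administrator named | Not stated |
| Re-operation | 1- and 2-year form, no time window | Not stated |
| Recurrence | 1- and 2-year form, new hernia or bulge | Only with a later examination (2.2) |
| Wound infection, treated collection, re-admission, bowel obstruction | No item in Appendix C | No |

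The last row matters because Section 1.1 names wound and adhesion-related complications as primary outcomes, and the instructions for use in Appendix B list seroma, hematoma, infection and bowel obstruction among possible events.

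**3. Illustration of size (assumed inputs).** The documents give neither an early complication rate nor a recording completeness. Assume that no false events are entered and N = 100.

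Expected reported rate = true rate × share recorded. Shortfall = true rate × (1 − share recorded).

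| True rate | Share recorded | Reported | Shortfall (points) | Coverage of exact 95% interval |
|---|---|---|---|---|
| 10% | 100% | 10% | 0 | 95.6% |
| 10% | 90% | 9% | 1 | 94.5% |
| 10% | 80% | 8% | 2 | 90.7% |
| 10% | 70% | 7% | 3 | 83.6% |
| 10% | 60% | 6% | 4 | 72.3% |
| 20% | 100% | 20% | 0 | 96.7% |
| 20% | 90% | 18% | 2 | 95.6% |
| 20% | 80% | 16% | 4 | 89.3% |
| 20% | 70% | 14% | 6 | 75.9% |
| 20% | 60% | 12% | 8 | 54.6% |

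At 90% recorded the effect on coverage is negligible. At 70% or below it is substantial. Nothing in the documents says where this registry lies.

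**The case against.** The strongest reply is that this is an open and legitimate registry choice. Data are collected under normal conditions of use (2.1), no additional visits are required (Section 7), and members who signed the Quality Charter are committed to its principles (2.2). That stands: leaving out source verification contradicts nothing, and the fix does not touch it. A signed commitment is still not a check.

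Second, Appendix C is a quality-of-life and satisfaction form, and the registry's complication forms are not shown. Sections 5.7 and 5.8 list complications separately, so more may be asked at 1 year than Appendix C shows. This limits the point to what is described, and the one described route depends on the patient complaining.

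Third, coherence analysis could set length of stay or patient answers against an empty complication field. Its scope is not specified, so it would be too strong to say that it can never find an omission. It cannot do so reliably.

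Fourth, some early outcomes do have input from others: nurse-assessed pain, patient-reported symptoms at 1 month, and the re-operation item, which could expose an unrecorded early re-operation. This also stands, but no section requires that answer to be compared with the surgeon's entry.

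A reader might also infer that under-recording exceeds the plan's ±5-point precision. The documents do not support this. That precision was set for a 5.9% recurrence rate; at 5.9%, recording 60–90% of events gives a shortfall of only 0.6–2.4 points. A shortfall above 5 points needs completeness below 1 − 5/20 = 75% at a true 20%, or below 1 − 5/30 = 83% at a true 30%, and none of these inputs is in the protocol.

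**Conclusion.** The point holds as a weakness in ascertainment; the protocol does not contradict itself here. Early complications are one part of a primary endpoint that runs to 2 years, and omissions among them have no reliable check. The independent calls could serve as a partial check but, as described, do not. The likely direction is under-counting. The size is unknown: the illustrated shortfalls of 1 to 8 points rest wholly on assumed true rates of 10–20% and recording of 60–90%.

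Two things rest on inference. That surgeon members enter the early complications follows from the account rule in Sections 2.2 and 7.2, although the associate also enters questionnaire answers. That resolved events go unasked follows from Appendix C and the footnotes to 5.7 and 5.8, without sight of the registry's other forms. It would go too far to conclude that the early results are wholly surgeon-assessed, or that surgeons do omit events; the documents show neither. The change is worth making because it costs little and makes completeness of a primary outcome partly measurable.

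**What to change.** Add one item to both calls, put to every patient: since the operation (at 1 year) or since the last contact (at 2 years), has there been any wound infection, treated fluid collection, re-admission, bowel obstruction, re-operation or other complication, and roughly when?

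Compare these answers, and the existing re-operation item, with the surgeon's entries. Send each mismatch to the surgeon as a data query; a patient report should not count as an event automatically. Beside the registry-reported incidence, give the number of patient-reported events absent from the surgeon's entries, split into confirmed and unresolved. Section 2.3 may keep its rule on source verification.

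The cost is one question in calls already planned and a short query list, with no extra visit or staff. The price is recall error, worst for minor events nearly a year old, and possibly a less favourable complication rate. The check remains partial: queries return to the surgeon who made the entry, and patients lost before the call are not covered (the plan expects 15% lost at 24 months).

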## **3. Product Description**

The product description and Instructions for Use are described in Appendix A & B.

Symbotex™ Composite Mesh is proposed in three configurations (flat mesh without preplaced suture yarns, flat mesh with preplaced suture yarns, and mesh with open skirt (flap).

Symbotex™ Composite Mesh is available in several shapes and sizes.

Symbotex™ composite mesh is intended for the reinforcement of abdominal wall soft tissue where a weakness exists, in procedures involving primary abdominal wall and incisional hernia surgeries. The non-absorbable three-dimensional Polyethylene terephthalate (polyester) mesh provides long term reinforcement of soft tissues. On the opposite side, the absorbable hydrophilic film minimizes tissue attachment to the mesh in case of direct contact with the viscera.

In addition, Symbotex™ Composite has been specifically designed for ease of use, for example:

- ✓ Presence of green marking for orienting and placing the mesh, the green drop-shaped marker in the center of the mesh helps the orientation and placement of the mesh to the medial line of the body.
- ✓ Mesh transparency for improved anatomy visualization during placement
- ✓ Conformability of textile for position against the abdominal wall

The Symbotex™ Composite Mesh will be CE marked and manufactured by the sponsor of the study, SOFRADIM PRODUCTION (subsidiary of Covidien).

## **4. Patient Selection**

The first one hundred consecutive adult patients scheduled for primary and incisional abdominal wall hernia surgery by Club Hernie members surgeons using Symbotex™

Composite Mesh (Flat sheet (SYM), Flat Sheet with sutures (SYM-F), with flap (SYM-OS) by open or laparoscopic approach. Patients' data will be reported in the Club Hernie database in real time.

#### **4.1 Inclusion Criteria**

- All patients regardless of gender  $\geq 18$  years of age presenting with ventral hernias.
- Patients will be informed by surgeon with a written information notice of the nature of the observational registry study.

#### **4.2 Exclusion Criteria**

No exclusion criteria outside the product IFU (Appendix B)

## **5. Clinical Assessments**

Patients will be followed using the online database for registration and patient outcome measurements, including pre-operative, operative and discharge data, post-operative course (D1 and D8 follow up), 1 month (D30 follow up), 1 Year and 2 Year follow up.

The study patients will be evaluated and the data will be recorded at time of consultation at the following time points.

### **5.1 Preoperative data**

- Demographic data (age, gender, ASA score, BMI, patient's occupation)
- Relevant prior medical/surgical history (previous surgical procedure including Hernia antecedents and abdominal surgical history) and comorbidities
- Hernia symptoms, disorders, region, discomfort and frequency

### **5.2 Operative data (D0)**

- Date of surgery
- Surgical technique approach
- Defect size, Hernia type and location
- Mesh size and type (SYM, SYMF; SYMOS)
- Amount of Overlap
- Type of fixation
- Operative time (from incision to closure, skin to skin), ,
- Mesh positioning and time

- Peri-operative events (including SAEs)
- Surgeon satisfaction (Mesh handling, mesh manipulability, ease of use)
- Pain assessment measured with VAS\* score (The pain nurse will carry out the pain evaluation)

\* VAS: The postoperative pain is assessed using a 0–10 Visual Analogue Scale.

Worst pain experienced over the last 24 hours.

### **5.3 Discharge data**

- Date of discharge
- Length of Hospital stay (number of nights in the institution after the surgery)
- Post-operative complications (including SAEs)

### **5.4 Post-operative course (D1) Follow up**

- Pain assessment measured with VAS score (The pain nurse will carry out the pain evaluation, either during systematic clinical visit or by phone call in case of day surgery)

### **5.5 Post-operative course (D8) Follow up**

Pain assessment measured with VAS score, either during systematic clinical visit or by phone call when a patient is already discharged.

### **5.6 1 month (D30) Follow up**

- Pain assessment measured with VAS\* score
- \* Mid pain for VAS score between 0 and 3; Moderate pain for VAS score > 3 and < 6 ; Severe pain for VAS scores > 6.
- Post-operative complications (including SAEs)
- Quality of Life « QoL » Questionnaire (Appendix C)

### **5.7 1 year follow-up**

- QoL and patient satisfaction Questionnaire (Appendix C)

- Post-operative complications (including SAEs)
- Pain assessment measured with VAS score\*

Follow-up at 1 year: All patients will be contacted by phone in order to complete a self-assessment questionnaire.

\*The patients who complained of any trouble will be invited to have a clinical visit at the surgeon's office. Post-operative complications and VAS score will be recorded.

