### **5.8 2 year follow-up**

- QoL and patient satisfaction Questionnaire (Appendix C)
- Post-operative complications (including SAEs)
- Pain assessment measured with VAS score\*

Follow-up at 2 year: All patients will be contacted by phone in order to complete a self-assessment questionnaire.

\*Patients who complain of any trouble will be invited to have a clinical visit at the surgeon's office. Post-operative complications and VAS score will be recorded.

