## **6. Statistical Methods**

### **6.1 Sample Size Calculation**

As described in the literature, the worst recurrence rate following incisional hernia repairs using synthetic mesh by laparoscopic and open approach, is 5.9 % [5] and 5.6 % [6] respectively.

Assuming a 95% confidence interval, a recurrence rate of 5.9 % with a +/- 5% precision, N=86 patients are needed for the Evaluable Population. Anticipating a 15% lost to follow up at 24 months, we plan to recruit a *minimum* of 100 patients for this observational registry as the Evaluable Population. Patients that are lost to follow-up or that withdraw consent will not be replaced.

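### At 1 and 2 years the VAS score is most naturally tied to the visit of patients who complain, and the phone form for everyone has neither a 0-10 pain item nor a prompt for most other complications

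*Protocol*

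**What the plan says.** The primary objective (Protocol 1.1) is the incidence of complications, including "pain, recurrence, complications related to adhesions, wound complications, other postoperative complications" and SAEs. The analysis summary in section 6.2 has "Primary endpoints measured within 1month, 1 Year and 2 Year follow-up".

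Sections 5.7 and 5.8 each list three assessments: the Appendix C questionnaire, post-operative complications including SAEs, and pain by VAS. All patients are phoned to complete the questionnaire. The VAS bullet alone carries an asterisk. Its footnote says "The patients who complained of any trouble will be invited to have a clinical visit" at the surgeon's office (5.8 has near-identical wording), and continues "Post-operative complications and VAS score will be recorded".

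Section 2.2 has the Clinical Research Associate enter the questionnaire answers. Clinical examination, and its comparison with the patient's answer, comes only after a complaint.

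The 1- and 2-year form in Appendix C asks about abdominal firmness, a new hernia or bulge, current discomfort (with moderate and severe pain among the options), its site, timing, frequency and effect on activity, comparison with the earlier hernia, "Have you had a re-operation on your abdominal wall", and an overall rating.

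**The concern.** Pain and complications at 1 and 2 years belong to the primary endpoint, yet the text does not say plainly who records them, or for whom, when a patient has no complaint to report.

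The two likely errors run in opposite directions. A VAS summary drawn mainly from people who came in because something was wrong overstates pain in the cohort. It also cannot be set against D30, where section 2.2 gives every patient an appointment. A complication that was treated elsewhere, or that has resolved, may never be mentioned if nobody asks, so its rate would be understated.

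This is a gap in collection, so a later analysis plan cannot close it: a score never asked for cannot be recovered. Section 2.3 also rules out source data verification, which might otherwise pick up missed events.

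**Working it through.** **1. What the sample size presupposes.** Section 6.1 gives the inputs: "Assuming a 95% confidence interval", and "a recurrence rate of 5.9 % with a +/- 5% precision, N=86 patients are needed". The precision formula is n = z² p(1 − p) / d², with z = 1.96, p = 0.059 and d = 0.05. This gives 3.8415 × 0.059 × 0.941 / 0.0025 = 85.3, rounded up to 86, so the stated figure is reproduced. With 100 recruited and 15% lost ("Anticipating a 15% lost to follow up at 24 months"), 100 × 0.85 = 85 patients remain, and the half-width is 1.96 × √(0.059 × 0.941 / 85) = 5.0 points. The sample size is not at issue here. It does presuppose an outcome known in about 85 patients.

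**2. Who supplies each outcome at 1 and 2 years.**

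| Outcome | Asked of every patient reached (Appendix C) | Otherwise |
|---|---|---|
| Recurrence | Yes: new hernia or bulge, with location | Examined if the patient complains and attends |
| Pain, categorical | Yes: discomfort, moderate pain, severe pain | – |
| Pain, 0-10 VAS | No item | Footnote links it to the complainers' visit |
| Abdominal-wall re-operation | Yes | – |
| Wound or mesh infection, mesh removal | No item | Listed in 5.7 and 5.8; method not stated for non-complainers |
| Bowel obstruction, other adhesion-related events | No item | Same |
| SAEs, hospital admission | No item | Same |

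The symptom questions concern what the patient feels now. Re-operation is the only question about a past event, and it is limited to the abdominal wall. The categorical pain item has no mild option and no link to the VAS bands in section 5.6, so it cannot stand in for the VAS. Sections 5.4 and 5.5 state that VAS may be taken by phone at D1 and D8; sections 5.7 and 5.8 do not.

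**3. Hypothetical size of the VAS bias.** The protocol gives neither the share who complain nor any VAS values. Assume that a share c complain and all attend, that their mean VAS is 4, and that the others would score 0.5. The cohort mean is then 4c + 0.5(1 − c).

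| c | Patients with VAS (85c) | Mean in attenders | Mean in whole cohort |
|---|---|---|---|
| 10% | 8.5 | 4.0 | 0.85 |
| 20% | 17 | 4.0 | 1.20 |
| 30% | 25.5 | 4.0 | 1.55 |
| 50% | 42.5 | 4.0 | 2.25 |

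If 50% of complainers and 2% of others exceed VAS 3 (also assumed), attenders show 50%. The cohort figure at c = 20% is 0.2 × 0.50 + 0.8 × 0.02 = 11.6%; at c = 10% and 30% it is 6.8% and 16.4%.

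**4. Hypothetical size of the complication bias.** Each event missed among 85 patients lowers a rate by 1/85 = 1.2 points, against the 5-point precision planned for recurrence. The documents give no basis for the number missed.

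**The case against.** A reader might infer that complications as well as VAS are recorded only in complainers, and that the long-term primary results therefore rest on a self-selected subset. The documents do not support that. The complications bullet has no asterisk, and the footnote nowhere says that other patients are excluded. Every patient reached is asked about bulge, categorical pain and abdominal-wall re-operation, by an associate independent of the surgeons and without medical adjustment. Recurrence, the outcome behind the sample size, thus has a patient-reported source in the full cohort.

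It can also be said that Appendix C is not the only route. Section 2.2 describes systematic entry of post-operative data by member surgeons, section 8 has device-related complications reported to the company, and the trigger for a visit is broad. Section 6.2 requires the number of missing values for quantitative variables, which would expose a small VAS count. The study is descriptive, with no success threshold.

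These points stand and limit the concern. They do not remove it. General statements about data entry do not say how an event treated elsewhere reaches the registry when the patient has no current complaint. Reporting a missing count shows that VAS is incomplete but does not correct the selection. No passage has VAS taken by phone at 1 or 2 years.

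**Conclusion.** The point holds for the VAS score, on the most natural reading of the footnote: a long-term summary would describe mainly symptomatic attenders, lean upward and not be comparable with D30. For complications other than recurrence and abdominal-wall re-operation it holds in a weaker form. They are listed for all patients, but nothing systematically prompts for them in patients who do not complain, so resolved or elsewhere-treated events may be missed and rates may lean downward.

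The size of either bias cannot be determined from the documents. The VAS figures above rest wholly on assumed complaint shares and pain levels, and the 1.2 points is a per-event unit rather than an estimate. The ambiguity about who records what is itself worth removing, because surgeons and the associate could apply the text differently.

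**What to change.** Reconcile sections 2.2, 5.7, 5.8 and Appendix C:

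- In 5.7 and 5.8, have the Clinical Research Associate ask every contacted patient for the 0-10 pain score by phone, the mode already allowed at D1 and D8.
- Add yes/no items covering the time since last contact to the 1- and 2-year form: hospital admission or abdominal operation, including for bowel obstruction; wound or mesh infection, or mesh removal; any other complication.
- Analyse the all-patient phone data as the endpoint, and use the data from complainers' visits as verification.

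The cost is one or two extra minutes in calls already planned and a small revision of the two sections and the form. No extra visit or staff is needed, so the change fits the statement in section 7 that the study requires no additional visits.
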